1.4 Required power for primary endpoint and noninferiority margin (if applicable)

The sample size calculation was based on both HbA1c and body weight endpoints. The assumed standard deviation for HbA1c and the coefficient of variance for body weight were 1.2% and 3%, respectively. The combined power (calculated as the product of the marginal powers for HbA1c and body weight) was at least 85%. Noninferiority of glycemic control with liraglutide versus glimepiride was concluded if the upper limit of the two-sided 95% CI for the treatment difference was < 0.4%.

With a standard deviation of 1.2% for HbA1c and a coefficient of variance of 3% for body weight, it was concluded that at least 168 subjects were required to complete the treatment in the liraglutide and in the glimepiride, respectively. Assuming a dropout rate of 25% after 26 weeks of treatment, the number of subjects to be randomized was calculated to be 228 in each of the liraglutide and glimepiride treatment groups.

1.5 Secondary endpoint for replication (assay sensitivity) and RCT finding n/a

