6.3.1 Outcome variables

Effectiveness outcome variables of interest (definitions provided in **Appendix A**):

• **Primary outcome:** Changes in HbA1c from baseline to 26 weeks of treatment (end of follow-up).

Note. In the trial, HbA1c was also measured at 8, 12, 18 weeks (± 3 days) after randomization. Missing values of HbA1c at 26 weeks were replaced using last observation carried forward (LOCF) in the intention-to-treat (ITT) analysis set. In the replication, HbA1c at baseline will be defined as the last recorded HbA1c value measured within 90 days before and including cohort entry date in both groups. HbA1c at the end of follow-up will be defined as a recorded HbA1c value closest to the end of the 26th week and measured between 56 and 212 days (8-30 weeks) after cohort entry.

Secondary outcome: --

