Optum CDM (binary HbA1c outcome [flag: presence or absence of an HbA1c result within 56-212 days after cohort entry]) – calculated merging the databases from $\frac{https://bwh-dope.aetion.com/projects/details/1688/rwrs/71715}{https://bwh-dope.aetion.com/projects/details/1688/rwrs/71715}$ and $\frac{https://bwh-dope.aetion.com/projects/details/1688/rwrs/71715}{https://bwh-dope.aetion.com/projects/details/1688/rwrs/71715}$

dope.aetion.com/projects/details/1688/rwrs/71716 – see file LEAD-2_programming_steps and output of "STEP 1 - Initial FEASIBILITY Analysis (with study outcome) - Paragraph 7 of the protocol"

Date conducted: 06/17/2021

Complete Aetion feasibility analysis using age and CCI as the only covariates and the primary endpoint (Section 6.3.1) as the outcome. No measures of association will be computed nor will mean and standard deviation of the HbA1c outcome stratified by treatment group.

• Report patient characteristics by treatment group For liraglutide vs. glimepiride

	Optum CDM		
	Glimepiride - Comparator	Liraglutide - Exposure	Difference
Number of patients *	3,096	378	- (-, -)
Age			
mean (sd)	64.24 (10.37)	59.22 (10.94)	5.02 (3.90, 6.13)
median [IQR]	67.00 [58.00, 72.00]	60.00 [51.00, 68.00]	- (-, -)
Gender			
M = MALE; n (%)	1,726 (55.7%)	179 (47.4%)	8.39% (3.08%, 13.7%)
F = FEMALE; n (%)	1,370 (44.3%)	199 (52.6%)	-8.39% (-13.7%, -3.08%)
Combined Comorbidity Score - CCI (180 days)			
mean (sd)	2.06 (1.56)	1.86 (1.36)	0.19 (0.03, 0.36)
median [IQR]	2.00 [1.00, 3.00]	2.00 [1.00, 2.00]	- (-, -)

^{*} The overall n. of patients in the unmatched cohort is 3,470. Patients who were censored between cohort entry and the beginning of the outcome assessment window (n. 290 patients) are excluded from the Table reporting patient characteristics by groups because they will not contribute to the unmatched or matched cohorts.

• Report summary parameters of study population **FEASIBILITY- FOR STUDY OUTCOME For** liraglutide vs. glimepiride

	Optum CDM
Number of patients in full cohort	3,764
Number of patients that did not begin follow-up *	290
Number of patients	3,474
Number of person-years of patients that did begin the follow-up	1,118.53
Number of patients in group: Glimepiride	3,096
Number of patients in group: Liraglutide	378
Outcome - Lab value HbA1c	
mean (sd)	7.24 (1.01)
median [IQR]	7.00 [6.60, 7.70]
minimum	4.1
maximum	13.4
Number of patients with zero value	0
Non-zero mean value (SD)	7.24 (1.01)

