Non-zero median value [IQR]	7.00 [6.60, 7.70]

^{*} patients who were censored between cohort entry and the beginning of the outcome assessment window/follow-up (i.e., 0.5-56 days after cohort entry) will not contribute to the unmatched and matched cohorts.

• Report median follow-up time by treatment group For liraglutide vs. glimepiride

Median Follow-Up Time (Days) [IQR] – AT analysis		
Patient Group Optum CDM		
Overall Patient Population	99 [84, 148]	
Referent	101 [84, 148]	
Exposure	88 [79, 130]	

• Report reasons for censoring in the overall study population

• For liraglutide vs. glimepiride

	Overall (n. 3,470)	Liraglutide (n. 378)	Glimepiride (n. 3,092)
Outcome *	2,262 (65.2%)	233 (61.6%)	2,029 (65.6%)
Death	2 (0.1%)	0 (0%)	2 (0.1%)
Start of an additional exposure	8 (0.2%)	3 (0.8%)	5 (0.2%)
End of index exposure	368 (10.6%)	74 (19.6%)	294 (9.5%)
Maximum follow-up time	336 (9.7%)	22 (5.8%)	314 (10.2%)
End of patient data	37 (1.0%)	3 (0.8%)	34 (1.1%)
End of patient enrollment	108 (3.1%)	12 (3.2%)	96 (3.1%)
Start of additional antidiabetic drugs + Nursing home + Metformin discontinuation with allowed 60 days gap	349 (10.1%)	22 (5.82%)	314 (10.2%)

^{*} patients with outcome recorded between 56-212 days after cohort entry.

• Report overall mean (sd) of the primary outcome.

	Optum CDM
Outcome – Lab value HbA1cmean (sd)	7.24 (1.01)

8. Initial Power Assessment

Analysis report name:

For liraglutide vs. glimepiride

Optum CDM – see file LEAD-2_programming_steps and output of "STEP 2 - INITIAL POWER Assessment - PS matching on age, gender, CCI (with dummy outcome) - Paragraphs 8 of the protocol"

Date conducted: 06/16/2021

In order to complete the initial power analysis, the dummy outcome of a 90-day gap in database enrollment will be used. This outcome is used to ensure that no information on the comparative risks of the outcomes of interest are available at this stage.

Complete a 1:1 PS-matched comparative analysis using this outcome. PS should include only 3 covariates: age, gender and combined comorbidity index. Power calculations are based on the formulas from Julios et al. (2008).

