• Stop analyses until feasibility and power are reviewed by primary investigators and FDA. Reviewers evaluate the results of the analyses described above in Sections 7 and 8, including numbers of patients, patient characteristics, follow-up time, and reasons for censoring by treatment group, as well as overall rates of outcomes and study power. These parameters are re-evaluated and reported in the subsequent sections, after incorporating feedback and refining the protocol.

o Optum CDM

Non-inferiority Analysis	
Standard deviation of outcome	1.01
Non-inferiority limit	0.4
Alpha (2-sided)	0.05
Power (1-beta)	90%
Sample size required per group	110
Total sample size required	220
Number of patients matched	752
Reference	376
Exposed	376

• Stop analyses until feasibility and power are reviewed by primary investigators, FDA, and assigned members of advisory board.

Reviewed by PI:	[name]	Date reviewed:	07/16/2021
Reviewed by FDA:	[name]	Date reviewed:	08/2/2021
Reasons for stopping			
analysis (if required):			

9. Balance Assessment

For liraglutide vs. glimepiride

Optum CDM: see file LEAD-2_programming_steps and output of "STEP 3 - BALANCE Assessment (with dummy outcome) - Paragraphs 9-10 of the protocol"

Date conducted: 06/16/2021

After review of initial feasibility and power analyses, complete creation of the remaining covariates from Section 6.2. Again, using the dummy outcome of a 90-day gap in database enrollment, complete a 1:1 PS-matched analysis. The PS should include the complete list of covariates.

• Provide plot of PS distributions stratified by treatment group.

Note- Please refer to Appendix B.

• Report covariate balance after matching.

Note- For Table 1, please refer to **Appendix B**.

• Report reasons for censoring by treatment group.

	Overall (n. 746)	Liraglutide – exposure (n. 373)	Glimepiride – comparator (n. 373)
Outcome (dummy)	0 (0%)	0 (0%)	0 (0%)
Death	0 (0%)	0 (0%)	0 (0%)
Start of an additional exposure	9 (1.2%)	6 (0.8%)	3 (0.4%)
End of index exposure	194 (26.0%)	137 (18.4%)	57 (7.6%)
Maximum follow-up time	340 (45.6%)	137 (18.4%)	203 (27.2 %)
End of patient data	5 (0.7%)	3 (0.4%)	2 (0.3%)
End of patient enrollment	61 (6.3%)	25 (3.4%)	36 (4.8%)
Start of additional antidiabetic drugs + Nursing home + Metformin discontinuation with allowed 60 days gap	137 (18.4%)	65 (8.7%)	72 (9.7%)

• Report follow-up time by treatment group.

Median Follow-Up Time (Days) [IQR]			

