Patient Group	Overall (n. 746)	Liraglutide (n. 373)	Glimepiride (n. 373)
Overall Patient Population	188 [97 - 212]	150 [89 - 212]	212 [119 -212]

• Report overall mean (sd) of the primary outcome (from initial feasibility analysis).

	Optum CDM
Outcome – Lab value HbA1cmean (sd)	7.24 (1.01)

10. Final Power Assessment

Date conducted:

• Re-calculate power in the appropriate excel table, using the revised number of matched patients from the PS-match in Section 9. All other parameters in the table should be the same as in Section 8.

Non-inferiority Analysis	
Standard deviation of outcome	1.01
Non-inferiority limit	0.4
Alpha (2-sided)	0.05
Power (1-beta)	90%
Sample size required per group	110
Total sample size required	220
Number of patients matched	746
Reference	373
Exposed	373

• Stop analyses until balance and final power assessment are reviewed by primary investigators, FDA, and assigned members of advisory board.

Reviewed by PI:	[name]	Date reviewed:	07/16/2021
Reviewed by FDA:	[name]	Date reviewed:	08/2/2021
Reasons for stopping			
analysis (if required):			

11. Study Confidence and Concerns

Deadline for voting on study confidence and listing concerns:

Date votes and concerns are summarized:

- If final feasibility and power analyses are reviewed and approved, proceed to the remaining protocol steps.
- All study team and advisory board members that review this protocol should at this stage provide their level of confidence for the success of the RWD study in the Google Form. This form also provides space for reviewers to list any concerns that they feel may

contribute to a failure to replicate the findings of the RCT, including differences in study populations, poor measurement of study variables, or residual confounding. All responses will be kept confidential and individual-level results will only be shared with the individual respondent.

• After the deadline for voting has passed, provide the distribution of responses and summarize all concerns here.

12. Register study protocol on clinicalTrials.gov

Date conducted:

• Register the study on clinicalTrials.gov and upload this document.

13. Comparative Analyses

Aetion report name:

Date conducted:

- 13.1 For primary analysis:
- 13.2 For sensitivity analyses:

14. Requested Results

14.1 Table 1: Baseline characteristics before and after adjustment

Variable	Before adjustment		After adjustment			
	Referent	Exposure	Std. diff.	Referent	Exposure	Std. diff.

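### The power tables in Sections 8 and 10 use the SD of the follow-up HbA1c level (1.01), but the primary endpoint is change from baseline, so the stated requirement of 110 per group is for a different variable

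*Combined protocol and SAP*

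**What the plan says.** Section 6.3.1 defines the primary outcome as "Changes in HbA1c from baseline to 26 weeks of treatment (end of follow-up"). Section 1.3 and the outcome row of Appendix A also define it as a change from baseline.

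Section 7 says that the feasibility run takes the Section 6.3.1 endpoint as its outcome. Its output is labelled as a laboratory HbA1c value, with mean 7.24, SD 1.01, median 7.00, minimum 4.1 and maximum 13.4. Section 9 repeats 7.24 (1.01) under the instruction "Report overall mean (sd) of the primary outcome (from initial feasibility analysis").

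The power table in Section 8 enters 1.01 as the "Standard deviation of outcome", with a margin of 0.4, alpha 0.05 labelled two-sided and 90% power, and states 110 per group. Section 10 repeats these entries and instructs: "All other parameters in the table should be the same as in Section 8". Only the matched number changes, from 376 to 373 per group.

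Section 1.4 reports that the trial being replicated was sized "With a standard deviation of 1.2% for HbA1c".

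**The concern.** A sample-size calculation for a difference in mean change needs the SD of the change, or the residual SD if the model adjusts for baseline. The SD of the follow-up level equals the SD of change only at one particular baseline to follow-up correlation, and the plan reports no correlation.

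The power assessment is a stop point: Sections 8 and 10 hold the analysis until the investigators, the regulator and advisory board members have reviewed it. Its main variability input should describe the declared endpoint. As written, those reviewers see 373 against 110 without knowing that the 110 belongs to another variable.

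**Working it through.** **Step 1. Which variable has SD 1.01?** A minimum of 4.1 cannot belong to a change score here, since every patient's HbA1c would have had to rise by at least 4.1 points. Mean baseline HbA1c in Appendix B is 8.16 (glimepiride) and 8.18 (liraglutide), so a follow-up mean of 7.24 implies a mean change of about 7.24 − 8.16 = −0.92. The figures 7.24 and 1.01 describe the follow-up level.

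**Step 2. Reproduce the stated 110.** Take a margin of 0.4, a true difference of 0 (an assumption; Section 1.6 reports 0.0% for the trial), 1:1 allocation and 90% power:

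n per group = 2 × (z_alpha + z_0.90)² × SD² / 0.4²

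- As labelled, two-sided 0.05 (z = 1.960 and 1.2816): n = 131.34 × SD². With SD 1.01, 131.34 × 1.0201 = 133.98, so 134.
- One-sided 0.05 (z = 1.645 and 1.2816): n = 107.05 × SD². With SD 1.01, 107.05 × 1.0201 = 109.2, so 110.

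The tables' 110 thus comes from one-sided 0.05. This error is separate from the choice of SD. The like-for-like starting point at the labelled alpha is 134.

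**Step 3. SD of change.** The inputs are follow-up SD 1.01 (Section 7) and baseline SD 0.96 (Appendix B, unmatched glimepiride arm, all patients; liraglutide is 0.99). The correlation r is not in the documents, so it is varied:

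SD_change = √(0.96² + 1.01² − 2r × 0.96 × 1.01) = √(1.9417 − 1.9392 r)

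This equals 1.01 when r = 0.96 / (2 × 1.01) = 0.475. With a baseline SD of 0.99 the break-even is 0.490.

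**Step 4. Requirement and power at two-sided 0.05.** The last column assumes that the observation rates in the Section 7 censoring table (unmatched cohort: 61.6% liraglutide, 65.6% glimepiride) apply to the matched cohort: 373 × 0.616 ≈ 230 and 373 × 0.656 ≈ 245. Power = Φ(0.4 / (SD × √(1/230 + 1/245)) − 1.960).

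| Assumed r | SD of change | Required n per group | Power with 230 and 245 observed |
|---|---|---|---|
| 0 | 1.39 | 256 | 87.8% |
| 0.1 | 1.32 | 230 | 90.9% |
| 0.2 | 1.25 | 205 | 93.8% |
| 0.3 | 1.17 | 179 | 96.2% |
| 0.4 | 1.08 | 154 | 98.1% |
| 0.5 | 0.99 | 128 | 99.3% |
| 0.6 | 0.88 | 103 | 99.9% |

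For comparison, SD 1.2 gives 131.34 × 1.44 = 189.1, so 190 per group.

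**Step 5. Where would power fall below 90%?**
- With 373 per group, only if the SD exceeds 0.4 / (3.2415 × √(2/373)) = 1.69. The SD of change at r = 0 is 1.39.
- With 230 and 245, only if the SD exceeds 0.4 / (3.2415 × √(1/230 + 1/245)) = 1.344, which corresponds to r = (1.9417 − 1.344²) / 1.9392 ≈ 0.07.

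**Step 6. If the contrast were adjusted for baseline.** The relevant SD would be 1.01 × √(1 − r²): 0.99 at r = 0.2 and 0.87 at r = 0.5. It never exceeds 1.01.

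**The case against.** The strongest reply is that nothing turns on it. The cohort is retrospective and of fixed size, so the requirement recruits nobody, and 373 per group exceeds even the 256 needed at r = 0. Under baseline adjustment 1.01 would be conservative. Both points stand, and they limit the finding to a wrong input in a review table. They do not make the input right: no adjusted model is specified, Section 13 is blank, and the results table in Section 14.4 is laid out for hazard ratios.

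A reader might infer more than the documents support:

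- **That the study is underpowered.** Steps 4 and 5 show otherwise over nearly the whole range, even counting only observed outcomes. Section 6.3.2 plans multiple imputation in the primary analysis, so the observed-only counts are a cautious reading.
- **That 1.01 is too small.** The direction is unknown without r.
- **That the trial's 1.2 settles it.** Section 1.4 calls this an SD for HbA1c and does not say that it is the SD of change.
- **That the requirement jumps from 110 to, say, 179.** That comparison mixes the alpha error with the SD error. Like for like at r = 0.3, it moves from 134 to 179.
- **That the SD of change already sits in the feasibility output.** Section 7 describes a run with only preliminary covariates. Baseline HbA1c appears in Appendix B, and the documents do not show a change variable in the Section 7 dataset.
- **That Section 10 bars any correction.** It carries the Section 8 inputs forward, but Section 8 also says that parameters are re-evaluated after feedback.

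**Conclusion.** The concern holds as an input error. Both power tables describe the variability of the follow-up level, whereas the plan's endpoint is change. For r from 0.2 to 0.6 the correct requirement at the labelled alpha lies between 205 and 103 per group, against 134 with SD 1.01, so the stated need could move either way. The 110 is additionally wrong for its label, because it results only from one-sided 0.05.

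The conclusion that the study is feasible probably survives. It would come into question only if the unmatched observation rates carry over to the matched cohort, imputation recovers little information, and r is below about 0.07. These sizes rest on an assumed r, a true difference of 0, a baseline SD taken from the whole unmatched cohort rather than from patients with an in-window value, and the normal approximation.

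**What to change.** In Sections 8 and 10:

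1. Replace 1.01 with the SD of follow-up minus baseline HbA1c among patients with an in-window value, pooled and not split by arm. This respects Section 7's rule against outcome summaries by treatment group.
2. Recompute the required n at the labelled two-sided 0.05, which also removes the discrepancy behind the 110.
3. Amend the Section 10 instruction so that the corrected SD is what is carried forward.
4. In Sections 7 and 9, label 7.24 (1.01) as the follow-up level and report the mean and SD of change beside it.

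Alternatively, if the treatment contrast is to be adjusted for baseline HbA1c, state that model in Section 13 and enter the pooled residual SD. In that case 1.01 can be kept as a conservative value, provided the plan says so.

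The cost is one pooled calculation, which needs baseline and follow-up values linked by patient, and edits to the two power tables and the wording around them. The stated requirement may rise or fall.

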6.3.2 Primary analysis and study follow-up

As-treated (AT) analysis will be performed as main analysis. The treatment drug will be defined as the index drug assigned on the day of cohort entry. Patients will be followed for about 30 weeks (212 days). Compared to the trial (Nauck M et al. 2009), we will

extend the follow-up and the outcome assessment periods of 4 weeks. The follow-up and outcome assessment window will start 56 days after cohort entry date and will continue until the earliest date of the following events:

- The first occurrence of the outcome of interest (measured between 56 and 212 days after cohort entry),
- The date of end of continuous registration in the database (disenrollment or end of available data),
- End of the study period,
- Measured death event occurs,
- Index drugs discontinuation (liraglutide, glimepiride or metformin),
- Crossover or addition of drug from the other treatment group,
- Addition of any other anti-diabetic medications,
- Nursing home admission
 - Nursing home admissions are considered a censoring event because the data sources utilized typically provide little to no data on a patient, particularly on drug utilization, after admission. We will utilize this as an exclusion reason for cohorts for the same reason.

Note. To decrease the incidence of missing values of the outcome (specifically, missing of HbA1c values measured between 56-212 days after cohort entry), we required that the eligible patients had at least 3 HbA1c measurements recorded within 365 days before and including cohort entry. This will increase the probability of including in the final cohort patients who are adherent to a routinely HbA1c testing and, consequently, will decrease the frequency of missing values of the outcome. Multiple imputation will be used to handle missing values in the primary analysis, while complete case analysis will be applied in a sensitivity analysis.

7. Initial Feasibility Analysis

Aetion report name:

For liraglutide vs. glimepiride

Optum CDM (continuous HbA1c outcome) https://bwh-dope.aetion.com/projects/details/1688/rwrs/71723

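### Sections 8 and 10 label alpha as two-sided 0.05 but give 110 per group, which is the one-sided 0.05 figure; with a true difference of 0 the stated inputs need 134 per group

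*Combined protocol and SAP*

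**What the plan says.** The table in Section 8 (Initial Power Assessment) gives an outcome SD of 1.01, a non-inferiority limit of 0.4, "Alpha (2-sided) 0.05" and "Power (1-beta) 90" per cent. From these it reports "Sample size required per group 110" and a total of 220, above the matched count of 376 per group.

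Section 10 (Final Power Assessment) updates only the matched count, to 373 per group. It instructs that "All other parameters in the table should be the same as in Section 8", so the 110 and 220 appear again.

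The only non-inferiority criterion in the document is in Section 1.4. It describes the original trial, where non-inferiority was concluded "if the upper limit of the two-sided 95% CI for the treatment difference was < 0.4" per cent. No separate decision rule for the replication is written. Neither power table states the true treatment difference that it assumes.

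**The concern.** A non-inferiority conclusion uses one end of the confidence interval. A two-sided alpha of 0.05 therefore puts 0.025 in the tail that matters, and the critical value is 1.960. The figure of 110 looked too small for that critical value and close to what 1.645 would give. If so, either the label or the number in each table is wrong.

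These tables are what the investigators, the FDA and the advisory board are asked to review before the analysis proceeds, and Section 12 has the document registered and uploaded. A reader who tries to reproduce the requirement from the listed inputs cannot do so. The error also flatters the margin of safety: 373/110 = 3.4 times the requirement, against 373/134 = 2.8 times.

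**Working it through.** **Inputs.** SD 1.01, limit 0.4, two-sided alpha 0.05 and power 90% come from the tables in Sections 8 and 10. The 1:1 matching comes from Section 8. The true difference is taken as 0; this is an assumption, consistent with the trial estimate of 0.0% in Section 1.6.

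**Formula.** n per group = 2 × (z_α + z_β)² × SD² / limit². Here 2 × 1.01² / 0.4² = 2.0402 / 0.16 = 12.751, and z_β = 1.2816 for 90% power.

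**Reproducing the plan's figure (one-sided 0.05).** (1.6449 + 1.2816)² × 12.751 = 109.20, rounded up to **110 per group, 220 in total**. This matches the tables exactly.

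**Using the label as printed (two-sided 0.05).** (1.9600 + 1.2816)² × 12.751 = 133.98, rounded up to **134 per group, 268 in total**. The shortfall is 134 − 110 = 24 per group, 48 in total, or 24/134 = 18%.

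**Other routes to 110 at two-sided 0.05:**

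| Variant | Result |
|---|---|
| 80% power | 101 per group |
| 85% power | 115 per group |
| t-distribution, 90% power | 135 per group |
| Equivalence formula | 138 per group |
| SD needed for 110 | about 0.915 (tables say 1.01) |
| True difference needed for 110 | about −0.04, favouring liraglutide (not stated) |

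With the t-distribution and one-sided 0.05 the answer is again 110. Among these variants, only one-sided 0.05 returns 110 without an input that the document does not contain.

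**Power under the two-sided 95% criterion.** Power = Φ(0.4 / (1.01 × √(1/n₁ + 1/n₂)) − 1.96).

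- 110 per group: Φ(2.937 − 1.960) = 83.6%.
- 134 per group: 90.0%.
- 373 per group: Φ(5.409 − 1.960) = 99.97%.

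**Allowing for missing outcomes.** Section 6.3.2 plans multiple imputation, so not every matched patient has an observed HbA1c. The Section 7 censoring table counts "patients with outcome recorded between 56-212 days after cohort entry": 233 of 378 on liraglutide and 2,029 of 3,092 on glimepiride. These rates are from the unmatched cohort, and applying them to the matched groups is an assumption. It gives 373 × 233/378 ≈ 230 and 373 × 2,029/3,092 ≈ 245, with power Φ(4.314 − 1.960) = 99.1%.

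**The case against.** The strongest reply is that the label may be the wrong entry. A non-inferiority test is one-sided, 110 is exactly the one-sided 0.05 answer, and the spreadsheet is not in the document. Section 1.4 reports the original trial's rule in the past tense, so a one-sided 0.05 planning alpha would contradict no written rule for the replication. This stands in part: the cause of the mismatch cannot be confirmed. But the two-sided label is printed in both tables, it agrees with the only criterion written down, and nothing in the document mentions a one-sided 0.05 test. If one-sided 0.05 was intended, the label would need correcting instead, and the replication would then be planned to a looser standard than the trial it emulates.

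A second reply is that 134 depends on a true difference of 0. That is correct and should be said.

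A third is that nothing turns on the error: matched numbers far exceed either figure, and the sign-off blocks in Sections 8 and 10 carry the same dates, which suggests one review round rather than two. This limits the importance of the point but does not make the tables right.

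Finally, 1.01 is the SD of the follow-up HbA1c level (Section 7), while the endpoint is change from baseline. So 134 is what the listed inputs imply, not necessarily the requirement for the endpoint itself. That is a separate matter.

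**Conclusion.** The concern holds. In both tables the alpha label and the required sample size are inconsistent. With the printed inputs, two-sided alpha of 0.05 and an assumed true difference of 0, the requirement is 134 per group (268 in total), not 110 (220). Under the two-sided 95% criterion, 110 per group would give 83.6% power.

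This is a correction to the record. The 373 matched per group exceed the corrected requirement, as do the roughly 230 and 245 expected to have an observed outcome. The feasibility decision, margin, cohort and analysis do not change.

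**What to change.** In the tables of Sections 8 and 10, replace 110 with 134 and 220 with 268, and add a note that the calculation assumes a true difference of 0. Check the spreadsheet at the same time to confirm which alpha was entered. Relabelling alpha as one-sided 0.05 would also make the tables consistent, but it would depart from the 95% confidence interval criterion in Section 1.4, so it is not the preferred repair.

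The cost is two cells in each of two tables and one sentence, with no extra patients and no change to the analysis.

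Two additions would help but are not part of the correction:

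- Note that 1.01 is the SD of the follow-up level, and either use the pooled SD of the change or add a row at the original trial's SD of 1.2. That row would read 2 × (1.9600 + 1.2816)² × 1.2² / 0.4² = 189.13, so 190 per group.
- Show the number with an observed outcome beside the 373 matched.
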